### **Power and Sample Size**

For our primary comparison of patient-level adherence across study arms, we expect to have 80% power to detect a 14.5 percentage point difference in patient-level adherence, assuming baseline adherence rates of 0.50 (SD 0.40) [based on our preliminary data], a two-sided alpha of 0.05, and a mean of approximately 3 opportunities for each patient to complete the survey. Based on prior trends in Beacon plan treatment starts in 2022, this assumes accrual of approximately 100 patients per month for three months totaling approximately n=300 patients. Over the course of the pragmatic trial, enrollment exceeded expectations at both participating sites. As such, the target accrual was updated to total approximately 480 patients.

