## CHARACTERISTICS OF THE STUDY POPULATION:

### 1. ***Target Population and Accrual:***

The target population will include approximately 480 patients with solid malignancies cared for at the following practice sites of the Penn Medicine Abramson Cancer Center (ACC), referred to hereafter as the “Implementation Laboratory”: **Perelman Center for Advanced Medicine (PCAM) and Princeton Health**. In this pragmatic trial, eligible patients will accrue as they initiate a new line of systemic cancer treatment.

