**STUDY DESIGN:**

**1. Study design:**

This hybrid type 2 study design will simultaneously evaluate implementation and effectiveness outcomes. We will conduct a three-arm randomized pragmatic trial to test the effect of patient reminders and triage nurse alerts, in the context of remote vs encounter-based PRO monitoring, on implementation and effectiveness outcomes. Participants meeting eligibility criteria will be randomized 1:1:1 to:

- (1) usual practice, consisting of encounter-based PRO monitoring;
- (2) encounter-based PRO monitoring plus patient reminders and triage nurse alerts;
- (3) remote PRO monitoring plus patient reminders and triage nurse alerts

Across arms, the administered PRO questionnaire will consist of 13 validated metrics spanning patient-reported symptoms, quality of life, and performance status. **[Appendix 1]** We will employ rapid cycle approaches to optimize implementation strategies prior to conducting the clinical trial.

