### **5. Statistical Analysis:**

#### **Aim 1**

The design is a three-arm randomized trial, resulting in three independent study arms: (1) usual practice, (2) encounter-based PRO monitoring with patient reminders and triage nurse alerts, (3) remote PRO monitoring with patient reminders and triage nurse alerts. Implementation and effectiveness outcomes will be assessed across arms. The main comparison for the purposes of power calculations will be Arm 2 vs Arm 1. Multivariable linear regression will be used to model patient PRO adherence as a function of nudge exposure (i.e., study arm assignment). Covariates will be assessed across study arms and included in the model if unbalanced across arms.

Significance will be determined using the z-score corresponding to each of the estimated effects, using a two sided type 1 error of 5%. All enrolled patients will be included in the intention-to-treat analysis.

The secondary outcomes will be similarly modeled except using logistic models as appropriate for binary outcome variables. All hypothesis tests will use a two-sided alpha of 0.05 as the threshold for statistical significance.

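### The stated 80% power for a 14.5-point difference at n=300 does not follow from the plan's inputs, which give 72–73%, and the detectable difference was not restated for 480 patients

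*Combined protocol and SAP*

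**What the plan says.** The Power and Sample Size section (under Study Procedures, 5. Statistical Analysis) holds the plan's only power statement for the primary outcome: "we expect to have 80% power to detect a 14.5 percentage point difference in patient-level adherence". Its inputs include "a mean of approximately 3 opportunities for each patient to complete the survey" and a 5% significance level, two-sided. The mean and spread of the outcome are stated as "assuming baseline adherence rates of 0.50 (SD 0.40) [based on our preliminary data". On sample size it says "this assumes accrual of approximately 100 patients per month for three months totaling approximately n=300 patients". It then reports that enrollment ran ahead of expectation and that "the target accrual was updated to total approximately 480 patients". The section on Target Population and Accrual carries the same number: "The target population will include approximately 480 patients with solid malignancies".

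Two other places fix the group sizes. Study Design, section 1, says "Participants meeting eligibility criteria will be randomized 1:1:1 to" the three arms, and the Aim 1 part of the Statistical Analysis section says "The main comparison for the purposes of power calculations will be Arm 2 vs Arm 1". The primary outcome is one value per patient, the proportion of expected questionnaires completed. It is analysed by linear regression and tested with a z-score.

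**The concern.** Every quantity needed for a standard two-group calculation is given: mean difference, SD, alpha, power, total n, allocation and the comparison. They do not fit together. With 100 per arm and SD 0.40, a 14.5-point difference falls short of 80% power by more than rounding can explain. Either the figure is wrong or an input that determines it has been left out.

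The sample size has also moved on. The statement describes a 300-patient design, the target is now about 480, and no power or detectable difference is given for the new number. A reader interpreting a null or modest Arm 2 vs Arm 1 result would have no valid detectable difference to set it against.

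**Working it through.** **Inputs.** SD 0.40, difference 0.145, two-sided alpha 0.05, power 80%, total 300 (Power and Sample Size); 1:1:1 allocation (Study Design), hence 300/3 = 100 per arm; Arm 2 vs Arm 1 (Statistical Analysis, Aim 1). Patients are randomized individually (Study Procedures, section 1), so no design effect is applied. No dropout, covariate gain, within-patient correlation or alpha adjustment is stated.

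**Attempt to reproduce the plan's figure at 100 per arm (normal approximation)**

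- Standard error of the difference = SD × √(2/n) = 0.40 × √(2/100) = 0.0566.
- Power at 0.145 = Φ(0.145/0.0566 − 1.960) = Φ(0.603) = 72.7%. The noncentral t gives 72.3%.
- Detectable difference at 80% power = (1.960 + 0.842) × 0.0566 = 0.1585, or 15.8 points. The noncentral t gives 15.9.
- Patients needed for 0.145 = 2 × (2.802 × 0.40/0.145)² = 119.5 per arm, so 120 (noncentral t: 120.4, so 121), or about 360 in total.
- SD that would make 0.145 correct = 0.145/(2.802 × √(2/100)) = 0.366 (noncentral t: 0.364).

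The stated 80% is not reproduced.

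**Can rounding explain it?** No. An SD of 0.395, the lowest value that rounds to 0.40, still gives 15.7 points. Combining SD 0.395 with a difference of 14.55 points gives only 74% power.

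**Can another design explain it?** Each of these was tried with the stated SD, or with the stated rates for the two-proportion test:

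| Variant | Power at 14.5 points |
|---|---|
| One-sided test | 82.1% (detectable 14.1 points) |
| Arms 2+3 pooled vs Arm 1 | 84.1% (detectable 13.7 points) |
| 300 split over two arms | 88.1% (detectable 12.9 points) |
| Bonferroni alpha 0.025 | 62.6% |
| Three-arm F test | 62–75%, depending on the pattern of means |
| Two proportions, 0.50 vs 0.645 | 54.5% |
| Arm 2 SD scaled to its mean | 74.5% (detectable 15.5 points) |

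None returns 80% at 14.5 points. The first three also contradict the stated two-sided alpha, comparison or allocation.

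**Can the three opportunities explain it?** Only with an unstated assumption. Suppose completions are exchangeable binary events at mean 0.50. This model is mine and is not in the documents. The variance of a patient's proportion over k opportunities is then 0.25 × (1 + (k − 1)ρ)/k. With three opportunities:

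- ρ = 0.30 gives SD = 0.5 × √(1.6/3) = 0.365, a detectable difference of 14.5 points and 80.2% power. This contradicts the stated SD of 0.40.
- SD 0.40 implies 1 + 2ρ = 3 × 0.16/0.25 = 1.92, so ρ = 0.46, and power is again 72.7%.

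The preliminary SD of 0.40 might come from a different number of opportunities, k. Solving for ρ at that k and recomputing the SD at three opportunities gives, at 100 per arm:

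| k behind SD 0.40 | ρ | SD at 3 opportunities | Detectable difference |
|---|---|---|---|
| 2 | 0.28 | 0.361 | 14.3 points |
| 2.07 | 0.30 | 0.366 | 14.5 points |
| 2.5 | 0.40 | 0.387 | 15.3 points |
| 3 | 0.46 | 0.400 | 15.8 points |
| 4 | 0.52 | 0.412 | 16.3 points |
| 6 | 0.57 | 0.422 | 16.7 points |

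Under this model 14.5 points is reached only if the SD came from about 2.1 opportunities per patient.

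**Current target, 480/3 = 160 per arm, SD 0.40**

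- Standard error = 0.40 × √(2/160) = 0.0447.
- Detectable difference = 2.802 × 0.0447 = 0.1253, or 12.5 points (noncentral t: 12.6).
- Power at 0.145 = Φ(0.145/0.0447 − 1.960) = Φ(1.282) = 90.0% (noncentral t: 89.8%).
- Over k = 2 to 6 in the model above, the detectable difference runs from 11.3 to 13.2 points and power at 14.5 points from 95% to 87%.

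**The case against.** The strongest reply is that the 72–73% calculation leaves out one listed input, the three opportunities per patient. The plan does not say whether the SD of 0.40 already reflects them. If it does not, 14.5 points may be the correct result of a repeated-measures calculation, and the sensitivity range above (14.3 to 16.7 points) does include it. A per-questionnaire SD of 0.40 with a within-patient correlation near 0.75 would also give it. So would covariates explaining about 16% of the variance (1 − (0.366/0.40)² = 0.163). On this view the figure is under-documented and has not been shown to be wrong.

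Part of that stands. The documents cannot settle which calculation was done, and the 7-to-8-point shortfall in power depends on 0.40 being the SD of the analysed outcome. That is the natural reading, however: the text attaches the SD to adherence rates in a sentence about patient-level adherence. If it is the SD over about three opportunities, those opportunities are already in it and cannot raise power a second time. No correlation or covariate gain is stated, and the analysis section admits covariates only where the arms are unbalanced.

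A second reply is that the consequence is small. The 300-patient design has been superseded, the increase is attributed to faster enrollment and not to power, and the plan makes no power claim for 480. All of this is correct. It limits the weight of the point but leaves the only power statement irreproducible and out of date.

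**Conclusion.** The concern holds. On the plan's stated inputs, with 0.40 taken as the SD of patient-level adherence, the 300-patient design has 72–73% power for 14.5 points, not 80%. Its detectable difference is 15.8–15.9 points, 1.3–1.4 above the stated figure. Recovering 14.5 points requires an assumption that the plan does not state, equivalent to an SD of about 0.364–0.366.

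The omission at 480 is real but runs in the safe direction: 14.5 points is conservative there. Power for that difference is about 90% at SD 0.40 and stays above 80% across the sensitivity range. The finding is therefore a correction to the documented justification and does not question the trial's current size. It should be fixed because this is the sole power statement for the primary outcome.

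**What to change.** First, make the n=300 statement reproducible, in one of two ways.

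- If 14.5 points came from a calculation using the three opportunities, keep it and disclose that calculation: the formula, the within-patient correlation or covariate gain used, how the three opportunities enter, and how many opportunities per patient lie behind the preliminary SD of 0.40.
- Otherwise correct it, for example: *For Arm 2 vs Arm 1 with 100 patients per arm (300 in total), SD 0.40 and two-sided alpha 0.05, power is 80% for a difference of about 15.8 percentage points and about 73% for 14.5 points.*

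Then add a sentence labelled as following the mid-trial increase in accrual, for example: *At the revised target of about 480 (160 per arm), under the same assumptions, power is 80% for a difference of about 12.5 percentage points and about 90% for 14.5 points.* If the disclosed assumption implies an SD other than 0.40, recompute this sentence with that SD.

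These figures use the normal approximation throughout, in line with the z-score test in the analysis section; the t-based values differ by about 0.1 point. The cost is one corrected and one added sentence, with no extra patients and no change to conduct or analysis.

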### **Aim 2**

We will evaluate for heterogeneity of implementation effects on PRO adherence by including an interaction term between study arm and, separately, patient-level age (dichotomized), sex, race/ethnicity, income, and geographic location. Evidence for effect modification will be judged based on the z-score corresponding to the ratio of hazard ratios (interaction term) using again a two-sided alpha of 0.05 as the threshold for statistical significance.

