## **OBJECTIVES:**

- (1) Evaluate the implementation and effectiveness of patient- and nurse-directed strategies across in-clinic and remote monitoring settings, using a three-arm pragmatic cluster RCT.
  - H1a: Nudges to patients and alerts to nurses will improve patient-level PRO completion and clinician-level PRO engagement
  
- (2) Evaluate moderators of implementation effects, using a quantitative evaluation of secondary data from the electronic health record, area-level data via geocoding, and clinician surveys.
  - H2a: The impact of nudges will be moderated by clinician, patient, and outer setting factors.
  - H2b: Baseline PRO adherence rates will differ by race, ethnicity, and socioeconomic status.
  - H2c: The nudge arms will not be significantly differentially effective across subgroups.

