## **BACKGROUND:**

Routine PRO monitoring is an evidence-based practice that improves patient outcomes. Patients with cancer commonly experience symptoms which go unrecognized by clinical teams up to half of the time. PROs are a powerful tool to bridge this gap, amplifying the patient experience and improving communication between patients and clinicians. Basch et al. conducted a seminal clinical trial in which weekly PRO symptom assessments with care team alerts led to reduced care utilization, improved quality of life, and lengthened overall survival among patients receiving active treatment for advanced solid tumors. Subsequent randomized trials have corroborated the quality of life and survival advantages of PRO monitoring in other cancer populations and practice settings.

Real-world adherence to PRO monitoring is lower than in seminal clinical trials, with potential racial/ethnic disparities. Multilevel barriers to PRO implementation exist at the patient, clinician, practice, and system levels. While patient adherence to PRO monitoring in seminal trials ranged from 70 to 90 percent, real-world adherence is much lower and more variable. Our preliminary research (under review) demonstrates that in a large, multi-site rollout of PRO monitoring, mean patient-level adherence was less than 50 percent. Moreover, compared to non-Hispanic White patients, Black and Hispanic patients were 9% and 4% less likely to complete PRO questionnaires, respectively, but more likely to report more severe symptoms. These results highlight that historically marginalized subgroups may benefit less from current methods of PRO administration, potentially reinforcing existing disparities in symptom management if not remediated.

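### Aim 2 assesses each moderator by one z-score, but three arms give two or more interaction coefficients per moderator, so the stated 5% level does not apply to the moderator as a whole

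*Combined protocol and SAP*

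**What the plan says.** The Aim 2 paragraph of the Statistical Analysis section examines heterogeneity of the effect on PRO adherence "by including an interaction term between study arm and, separately, patient-level age (dichotomized), sex, race/ethnicity, income, and geographic location". Its criterion is: "Evidence for effect modification will be judged based on the z-score corresponding to the ratio of hazard ratios (interaction term"). The threshold for that z-score is the one already set for Aim 1: "using again a two-sided alpha of 0.05 as the threshold for statistical significance". It names no joint test, no reference arm or category, and no adjustment over moderators. Age is the only factor whose coding is given.

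The Study Design section sets up three arms: "Participants meeting eligibility criteria will be randomized 1:1:1 to" usual practice and two nudge arms. The Aim 1 analysis fixes the outcome model: "Multivariable linear regression will be used to model patient PRO adherence as a function of nudge exposure (i.e., study arm assignment").

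The Objectives section states two hypotheses that this analysis has to serve: "H2a: The impact of nudges will be moderated by clinician, patient, and outer setting factors" and "H2c: The nudge arms will not be significantly differentially effective across subgroups". Neither comes with a decision rule.

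**The concern.** One z-score tests one coefficient. In a three-arm trial, the question whether a factor modifies the effect of arm has at least two degrees of freedom, and more if the factor has more than two categories. An analyst following the text must either pick one coefficient, which leaves the choice of contrast and reference category open, or read all of them at 0.05, which raises the error rate for the moderator above 5%. The inflation is largest for race/ethnicity, the factor central to the equity rationale in the Background.

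The problem is separate from the mention of hazard ratios. That wording does not fit a linear model, but correcting it to a linear interaction coefficient would leave the number of coefficients unchanged.

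**Working it through.** **Inputs.** From the documents: three arms, 1:1:1; five moderators in separate models; two-sided 0.05; linear model; adherence SD 0.40; about 480 patients, so 160 per arm. Assumed, because the plan does not define them: race/ethnicity with 3 or 4 levels (the Background names three groups: "compared to non-Hispanic White patients, Black and Hispanic patients were 9% and 4% less likely to complete PRO questionnaires"), and binary income and location. Other codings are shown in step 4.

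**1. The plan's own figure.** For one coefficient, P(|Z|>1.96) = 5.0%. The stated level is right for a single 1-df term. The plan gives no other error rate, and no power, for Aim 2.

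**2. Number of coefficients.** (3-1)(k-1) = 2(k-1) per moderator: 2 for a binary factor, 4 for three levels, 6 for four levels. Over five moderators, four of them binary, this is 4×2+4 = 12 or 4×2+6 = 14.

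**3. Error per moderator when every coefficient is read.** For a binary factor, let d1, d2, d3 be the between-group differences in the three arms, each with variance v. The two coefficients, d2-d1 and d3-d1, each have variance 2v and covariance v, so their correlation is 0.5. Then P(either |z|>1.96) = 9.1%; with independence it would be 1-0.95² = 9.75%. The SD and sample size cancel. Simulation of null trials at N=480 agrees:

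| Moderator | Any coefficient \|z\|>1.96 | One joint F test |
|---|---|---|
| Binary | about 9% | about 5% |
| Race/ethnicity, 3 levels | 16-17% | about 5% |
| Race/ethnicity, 4 levels | 21-25% | about 5% |

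The ranges reflect equal and unequal category sizes.

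**4. Five moderators, under a rule the plan does not contain.** Suppose any one significant coefficient counted as support for H2a. With independent moderators the rate is 1-(1-0.091)⁴(1-p), where p is the race/ethnicity rate. For p = 0.17 this is 1-0.683×0.83 = 43%; for p = 0.25 it is 1-0.683×0.75 = 49%. Simulated results at N=480:

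| Reading | At least one flag |
|---|---|
| Race/ethnicity 3 levels, others binary | 42.4-44.6% |
| Race/ethnicity 4 levels, others binary | 46.2-48.5% |
| Correlated moderators (latent r 0.3; 3 and 4 levels) | 42.5%; 47.7% |
| Arm 2 vs Arm 1 coefficients only, race/ethnicity 2-5 levels | 23-35% |
| Race/ethnicity 5 levels, others binary | 54.2% |
| Race/ethnicity 4, income 4, location 3 levels | 60.0% |
| One joint test per moderator | about 20-23% |
| Joint tests, each at 0.01 (first Holm step) | about 5% |

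The last two rows match 1-0.95⁵ = 22.6% and 1-0.99⁵ = 4.9%. About 23% is therefore the price of testing five moderators at 0.05, not of the single z-score.

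**5. Power of the joint test.** Take an effect 14.5 points smaller in one subgroup in both nudge arms, where that subgroup has share s. The noncentrality is 160·s(1-s)·(2/3)·0.145²/0.40².

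- Binary, s = 0.5: 160×0.25×0.01402/0.16 = 3.50 on 2 df. Power is 37% at 0.05 and 17% at 0.01.
- Race/ethnicity, subgroup with an assumed 20% share: 160×0.16×0.01402/0.16 = 2.24. Power at 0.05 is 19% on 4 df (3 levels) and 16% on 6 df (4 levels); at 0.01 it is about 6% and 5%.

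**The case against.** **The overall figure.** A reader might infer that H2a would be supported by chance in 42-48% of trials with no moderation. The documents do not support that as a plain statement. Aim 2 speaks of evidence moderator by moderator, the Objectives give no rule for how many positive terms support H2a, and only age is said to be dichotomized. Nor is the whole figure due to the single z-score. This objection stands, and the overall rate is given here only conditionally.

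**Fewer coefficients.** The plan calls Arm 2 vs Arm 1 its main comparison, and on that contrast alone a binary moderator has one coefficient and one z-score is enough. But the contrast is named for power calculations, and Aim 2 does not restrict itself to it. Three-level race/ethnicity would still have two coefficients, with an error of about 9% for equal group sizes by the same correlation of 0.5. Entering arm as a 1-2-3 score would also give one term for a binary factor, but it imposes a trend on unordered arms and still leaves several terms for race/ethnicity.

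**Adjustment over moderators.** These are Aim 2 analyses; the primary outcome is tested in Aim 1. Holm would lower interaction power that is already small, and H2c is read from non-significance, so lower power makes it easier to claim. This stands: adjustment is a choice with a price, and an exploratory label would deal with the multiplicity equally well.

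**Scope of H2a.** It includes clinician factors, and Aim 2 tests none. Better tests of the five listed factors cannot settle that part.

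**Conclusion.** The concern holds per moderator. The stated criterion does not test a moderator in a three-arm trial. Reading each coefficient at |z|>1.96 gives about 9% error for a binary factor, whatever the SD or sample size, and about 16-25% for race/ethnicity if it has 3-4 categories. A joint test restores about 5%.

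The rate over all five moderators is illustrative. It is about 42-48% with 3-4 race/ethnicity levels, binary income and location, both nudge contrasts read, and any single hit taken as support for H2a. Other readings compatible with the text give about 23-60%.

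The point affects a stated secondary aim and leaves the primary comparison untouched. It should be corrected before the Aim 2 analysis is run.

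**What to change.** In the Aim 2 paragraph of the Statistical Analysis section:

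- Replace the single z-score with one joint Wald or F test per moderator of all arm-by-moderator coefficients from the linear model, at two-sided 0.05: 2 df for a binary factor, 2(k-1) df for a k-level factor. This also removes the hazard-ratio wording, and the result does not depend on the reference arm or category.
- Fix in advance the categories of race/ethnicity and the coding of income and geographic location, including the age cut-point.
- Report Arm 2 minus Arm 1 and Arm 3 minus Arm 1 differences within each subgroup, with 95% CIs.
- For multiplicity over the five moderators, either label Aim 2 exploratory or adjust, for example by Holm, as the sponsor prefers.
- State what would count as support for H2a, and that a non-significant interaction does not confirm H2c; the subgroup CIs should carry that discussion.

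The cost is wording and a few lines of code, with no change to trial conduct. The joint test has less power for an interaction confined to one arm or category. Holm would reduce power further, as step 5 of the working shows.

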### **Aim 2**

Aim 2 measures, collected through the electronic medical record and using publicly available U.S. Census data, will include:

- *Patient-level data*: age, sex, race/ethnicity, education, marital status, cancer type, cancer stage, health insurance (e.g., Medicare, Medicaid, commercial);
- *Clinician-level data*: years in practice and patient panel size;
- *Practice-level data*: setting (community vs. hospital-based), urban vs. non-urban location, and health insurance mix;
- *Ecologic-level data* linked at the patient- and practice-level, including median income and educational attainment.

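### Age is split in two, at a cut the plan does not give, for the arm-by-age test; if the interaction is roughly linear, this costs that one secondary test power

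*Combined protocol and SAP*

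**What the plan says.** Statistical Analysis, Aim 2, looks for heterogeneity in PRO adherence by adding an interaction between study arm and, "separately, patient-level age (dichotomized), sex, race/ethnicity, income, and geographic location". Each interaction is judged "using again a two-sided alpha of 0.05 as the threshold for statistical significance".

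Age is the only moderator whose form is specified, and no cut-point, rule such as the median, or reason for splitting is given there or elsewhere. Data Collection, Aim 2, lists the patient-level measures as "age, sex, race/ethnicity, education, marital status, cancer type, cancer stage, health insurance", with no age categories. The Protected Health Information list includes date of birth, so the split is a choice of analysis and not a limit of the data.

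Two of the Aim 2 hypotheses under Objectives bear on this test. H2a says that "The impact of nudges will be moderated by clinician, patient, and outer setting factors". H2c predicts that the nudge arms will not differ significantly in effect across subgroups.

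**The concern.** Dichotomising treats all patients on one side of the cut as alike. If the arm effect drifts gradually with age, the contrast between two age groups captures only part of that drift, and the test is weaker than it need be.

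That matters here because H2c is worded so that a non-significant interaction counts in its favour. A weaker test makes that result easier to obtain whatever the truth, and makes the moderation predicted by H2a harder to find.

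The missing cut is a second problem. With a continuous variable and no stated threshold, different cuts can give different p-values, and nothing in the plan prevents the choice from being made after results are seen.

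**Working it through.** **Inputs from the documents.** Two-sided alpha is 0.05 (Statistical Analysis, Aim 2). For the model, "Multivariable linear regression will be used to model patient PRO adherence as a function of nudge exposure" (Aim 1). The Aim 2 paragraph refers to a ratio of hazard ratios, which does not belong to a linear model; I take the interaction to be fitted in the Aim 1 linear model. The SD of adherence is 0.40 and the target is 480 patients (Power and Sample Size), which at 1:1:1 (Study Design) is 160 per arm. For power, "The main comparison for the purposes of power calculations will be Arm 2 vs Arm 1".

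**Not in the documents, so assumed and varied.** These are the age distribution, the shape of the age interaction, and any power figure for Aim 2.

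**1. The plan's own power figure.** The only one is for the primary comparison: "80% power to detect a 14.5 percentage point difference in patient-level adherence", at about 300 patients. A simple two-mean calculation with 100 per arm gives SE = 0.40 × √(2/100) = 0.0566, so 0.145/0.0566 = 2.563 and power = Φ(2.563 − 1.960) = 72.7%. At 160 per arm it gives 90.0%. The 80% is not reproduced this way; an unstated adjustment for the roughly three questionnaire opportunities could explain the gap. That is a separate matter, and the figure is not used below.

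**2. Information kept by a split.** For a linear interaction this is the squared correlation between age and its two-group indicator, and it is the same for each arm contrast. With a fraction p below cut c:
- normal age: φ(c)²/[p(1−p)]; at the median, 0.3989²/0.25 = 0.637
- uniform age: 3p(1−p); at the median, 0.75

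| Split | Normal: kept | Normal: lost | Uniform: kept | Uniform: lost |
|---|---|---|---|---|
| 50/50 | 63.7% | 36.3% | 75.0% | 25.0% |
| 40/60 | 62.2% | 37.8% | 72.0% | 28.0% |
| 30/70 | 57.6% | 42.4% | 63.0% | 37.0% |
| 20/80 | 49.0% | 51.0% | 48.0% | 52.0% |

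For normal age the median is the least costly cut. Simulated median-split losses for other illustrative shapes are about 35% (normal truncated to 18–90), 38% (left-skewed), 30% (beta(2,2)) and 24% (bimodal).

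**3. Effect on power (hypothetical start of 80%).** The expected z of 1.960 + 0.842 = 2.802 is multiplied by √(information kept):
- normal, median split: 2.802 × 0.798 = 2.235; Φ(0.275) = 61%
- normal, 30/70: 2.802 × 0.759 = 2.126; Φ(0.166) = 57%
- uniform, median split: 2.802 × 0.866 = 2.426; Φ(0.466) = 68%

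Under normal age and a median split, 160 per arm act like 160 × 0.637 ≈ 102.

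**4. On the plan's own scale.** For Arm 2 vs Arm 1 with a median split there are 80 patients per arm in each age half. The interaction SE is 0.40 × √(4/80) = 0.0894, so 80% power needs a difference of 2.802 × 0.0894 ≈ 25 points between the arm effects in the two halves. For an illustrative 14.5-point difference:
- split: 0.145/0.0894 = 1.621; Φ(1.621 − 1.960) = 37%
- continuous, normal age, linear: 1.621/0.798 = 2.032; Φ(2.032 − 1.960) = 53%

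The test is weak either way, and weaker with the split.

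**The case against.** The strongest reply is that the loss depends on a shape nobody knows. The squared correlation is symmetric: if moderation is a step at the median and age is normal, the split loses nothing, and a linear test is the one that keeps only 64%. That is correct, and it means continuous age is not better in every case. But a split gains this advantage only if the cut sits at the true threshold, and the plan names neither a cut nor a reason to expect a threshold.

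A reader might infer that the split discards over a third of the information as a matter of fact. The documents do not support that, because they give neither an age distribution nor an interaction shape; a uniform or bimodal age distribution gives about a quarter at a median split.

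The 80% starting power is also not a figure from the plan. By the same formula, under normal age and a median split, a test starting at 30% falls to about 21%, a smaller absolute drop.

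Finally, age is one of five moderators, each tested separately, so its coding does not touch the tests for sex, race/ethnicity, income or location. Reading non-significance as support for H2c is a wider problem that continuous age would not cure. Both points stand, and they limit the importance of the concern.

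**Conclusion.** The concern holds in a limited form, as a minor improvement to one secondary moderator test. The text is clear: age is dichotomised, the cut is unstated, and exact age is obtainable.

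The size is conditional. With a roughly linear interaction, the loss is about 36% or more at any cut if age is near normal, and about 24% to 38% at a median split across the age shapes tried. It passes 50% at a 20/80 cut under normal or uniform age. With a step exactly at the cut, it is zero.

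A reader might go further and say that the split biases Aim 2 toward finding no differential effect, or that the cut was picked from the data. Neither is supported. The effect is lower power for the age interaction, which does not bias the other Aim 2 results, and the documents say nothing about how or when the cut is chosen. The primary analysis is unaffected.

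**What to change.** In Statistical Analysis, Aim 2, replace the dichotomised age term with age in years. Pre-state the arm-by-age interaction with a linear age term as the test. Add a spline version as a sensitivity check, with its knots fixed in advance and the linear term remaining the formal test if the two disagree, so that no new freedom is introduced. Report the estimated arm effects, with confidence intervals, at a few stated ages. Show age groups only as a descriptive display, at a cut written down before analysis. If the dichotomised test is kept instead, state the cut and the reason for it before analysis.

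The cost is a few sentences of text, with no new data or patients. The one statistical downside is some loss of efficiency if the true effect is a threshold: under normal age and a step at the median, the linear test keeps about 64% of the information. The spline check would help to reveal such a pattern.
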